9.4.2. Double-Blind Treatment Period

9.4.2.1. Visit 2 (Day 1) – Enrollment and Randomization

Subjects who continue to meet study eligibility requirements will be enrolled and randomized during Visit 2 (Day 1).

The following assessments will be performed during Visit 2 (Day 1):

- Complete [REDACTED]
- Confirm that the UAS and [REDACTED] were completed daily from the last visit through the morning of Visit 2 (Day 1)
- Vital signs
- Standard 12-lead ECG
- Concomitant medication usage assessment
- AE assessment
- Eligibility check
- Blood and/or urine sample collection for PD, safety, PK, and baseline characterization laboratory assessments
- Randomization to study drug treatment assignment via IWRS:
 - Part 1: 50 mg EP262, 150 mg EP262, or placebo in a 1:1:1 ratio
 - Part 2: 25 mg EP262 or placebo in a 3:1 ratio
- Dispense study drug
- Upon completion of the assessments listed above, study drug is to be administered PO as intact capsules (swallowed whole, not split, opened, or chewed) and taken with approximately 240 mL (8 fluid ounces) of water on an empty stomach

9.4.2.2. Visit 3 (Week 3)

The following assessments will be performed during Visit 3 (Week 3):

- Complete [REDACTED]
- Confirm that the UAS and [REDACTED] were completed daily from the last visit through the morning of Visit 3 (Week 3)
- Confirm that the [REDACTED] was completed weekly from the last visit through Visit 3 (Week 3)
- Collect study drug
- Assess study drug accountability and compliance

- Vital signs
- Concomitant medication usage assessment
- AE assessment
- Blood and/or urine sample collection for PD, safety, and PK laboratory assessments
- Dispense study drug
- Upon completion of the assessments listed above, study drug is to be administered PO as intact capsules (swallowed whole, not split, opened, or chewed) and taken with approximately 240 mL (8 fluid ounces) of water on an empty stomach

9.4.2.3. Visit 4 (Week 6)

The following assessments will be performed during Visit 4 (Week 6):

- Complete [REDACTED]
- Confirm that the UAS and [REDACTED] were completed daily from the last visit through the morning of Visit 4 (Week 6)
- Confirm that the [REDACTED] was completed weekly from the last visit through Week 5
- Collect study drug
- Assess study drug accountability and compliance
- Body weight
- Vital signs
- Standard 12-lead ECG
- Concomitant medication usage assessment
- AE assessment
- Blood and/or urine sample collection for PD, safety, and PK laboratory assessments

9.4.3. Safety Follow-Up Period

9.4.3.1. Visit 5 (Week 10)

The following assessments will be performed during the Safety Follow-Up Visit, approximately 4 weeks after the last dose of study drug:

- Complete the [REDACTED]
- Confirm that the UAS and [REDACTED] were completed daily from the last visit through the morning of Visit 5 (Week 10)
- Confirm that the [REDACTED] was completed weekly from the last visit through Week 9
- Body weight
- Vital signs

- Standard 12-lead ECG
- Concomitant medication usage assessment
- AE assessment
- Blood and/or urine sample collection for PD, safety, and PK laboratory assessments

9.4.4. Early Treatment Termination Visit

Subjects who discontinue from treatment early should have the Early Treatment Termination Visit conducted as soon as possible after the last dose of study drug, ideally within 2 days after the last dose of study drug. The following assessments will be performed during the Early Treatment Termination Visit:

- Complete [REDACTED]
- Confirm that the UAS and [REDACTED] were completed daily from the last visit through the morning of the Early Treatment Termination Visit
- Confirm that the [REDACTED] was completed weekly from the last visit through the Early Treatment Termination Visit
- Collect study drug
- Assess study drug accountability and compliance
- Body weight
- Vital signs
- Standard 12-lead ECG
- Concomitant medication usage assessment
- AE assessment
- Blood and/or urine sample collection for PD, safety, and PK laboratory assessments

10. STUDY DRUG MATERIALS AND MANAGEMENT

10.1. Study Drug

In Part 1, capsules containing 25 mg of EP262, 75 mg of EP262, or placebo will be supplied in bottles in a manner to ensure the study blind. Each subject will take 2 capsules per dose.

[REDACTED]

10.2. Study Drug Packaging and Labeling

Study drug will be packaged into bottles labeled with a unique number and supplied to clinical sites in a blinded manner.

10.3. Study Drug Storage

The study drug capsules should be stored at controlled room temperature, 15°C to 25°C (59°F to 77°F), with excursions up to 30°C (86°F).

10.4. Study Drug Administration

Each study drug dose is to be administered PO as intact capsules (swallowed whole, not split, opened, or chewed) and taken with approximately 240 mL (8 fluid ounces) of water on an empty stomach. Subjects will be instructed to take the study drug at approximately the same time of the day after a fast of at least 4 hours. Subjects should refrain from eating for at least 2 hours postdose. On the days of clinic visits, the time of study drug administration may differ depending on the scheduled visit time. The first dose of study drug will be administered at the clinical site on Visit 2 (Day 1) after all baseline study procedures are completed.

10.4.1. Instructions for Missed Dose(s)

Subjects should be instructed that if they forget to take a dose, they can take the dose within 8 hours of the normal dosing time; otherwise, they should take their next dose at the regular time on the following day. If the subject vomits the capsules, he/she should be instructed not to take additional capsules on the same day but to take the next dose at the regular time on the following day. Subjects should be instructed to contact the Investigator if they miss 2 or more consecutive doses.

10.5. Study Drug Dispensing and Accountability

Subjects will record self-administration of study drug daily in a dosing diary that will be reviewed at each clinical site visit during the Double-Blind Treatment Period by site staff.

Subjects should be instructed to retain the study drug, including the study drug bottle, even if empty, and to return it and any remaining study drug to the clinical site at their next visit. The site staff should perform study drug accountability and, if applicable, follow-up with the subject to retrieve any remaining study drug that has not been returned.

10.6. Study Drug Handling and Disposal

Study drug will be sent to the clinical site under appropriate storage conditions. Upon receipt of study drug, site staff are to open the shipment, and verify that the amount and identity of the contents match that stated in the enclosed shipping form. The Sponsor (or designee) is to be notified immediately about any irregularities, discrepancies, or damage.

Study drug will be provided for use only in this study and is not to be used for any other purpose. The site staff will maintain a full record of study drug accountability as described in Section 10.5.

Upon completion of the study, used and unused study drug and study drug bottles are to be returned to the Sponsor (or designee) or, if prior Sponsor approval is obtained, disposed of in accordance with applicable site procedures. Site staff must maintain documentation of any missing or unreturned study drug. The final disposition of all study drug received at the site is to be documented.

10.7. Product Quality Complaints

A product quality complaint (PQC) is defined as any suspicion of a product defect or deficiency related to manufacturing, labeling, or packaging (ie, any dissatisfaction relative to the identity, quality, durability, reliability, safety, effectiveness, or performance of a product, including its labeling or package integrity). A PQC may have an impact on the safety and efficacy of the product. Timely, accurate, and complete reporting and analysis of PQC information from studies are crucial for the protection of subjects.

All initial PQCs must be reported to the Sponsor or CRO by clinical-site personnel within 24 hours after being made aware of the potential defect. Whenever possible, the associated product should be maintained in accordance with the label instructions pending further guidance from the Sponsor.

[figure not shown]
11. EFFICACY ASSESSMENTS

[figure not shown]
The primary efficacy evaluation is based on the UAS, a patient-reported assessment of disease activity. Secondary efficacy evaluations include assessments of itching (ISS) and hives (HSS), both of which comprise the UAS. Exploratory efficacy evaluations include [REDACTED]

[figure not shown]
[REDACTED] All efficacy assessments will be performed as indicated in the Schedule of Assessments ([Appendix A](#)).

Examples of the patient-reported assessments are provided in the appendices but are not to be distributed to subjects for completion. Subjects will be trained on completion of all patient-reported assessments using the study-issued electronic device or application (app).

All subjects who were given a study-issued device, including those who fail Screening, will be required to return it to the site once their participation in the study is complete.

12. SAFETY ASSESSMENTS

Safety evaluations, including AEs, concomitant medications, medical history, vital signs, physical examinations, standard 12-lead ECGs, and laboratory evaluations of safety will be performed as indicated in the Schedule of Assessments ([Appendix A](#)).

12.1. Adverse Events

12.1.1. Definition of an Adverse Event

An AE is defined as any untoward medical occurrence in a subject administered a pharmaceutical product and which does not necessarily have a causal relationship with this treatment. An AE can therefore be any unfavorable or unintended sign (including a clinically significant abnormal laboratory finding), symptom, or disease temporally associated with the use of a medicinal (investigational) product.

Medical conditions present at baseline that worsen in severity or frequency after exposure to study drug are considered TEAEs. A TEAE is any condition that was not present prior to treatment with the study drug but appeared following treatment, was present at treatment initiation but worsened during treatment, or was present at treatment initiation but resolved and then reappeared while the individual was on treatment (regardless of the intensity of the AE when the treatment was initiated). Planned hospital admissions or surgical procedures for an illness or a disease that existed before administration of study drug, and for which the condition has not worsened since starting study drug, are not to be considered TEAEs/treatment-emergent SAEs. Events with emergency room visits that are less than 24 hours will also not be considered SAEs unless they meet one of the criteria listed in Section [12.2.1](#).

Clinically significant abnormal laboratory tests, 12-lead ECG assessments, or vital sign results may constitute an AE if they meet one of the criteria listed in Section 12.1.4.1. However, whenever possible, the underlying diagnosis should be listed in lieu of associated abnormal results. Abnormalities deemed not clinically significant by the Investigator should not be reported as AEs.

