8.1. Subject Inclusion Criteria

To be eligible for study participation, all subjects must meet all of the following inclusion criteria:

1. Male or female subject, aged 18 to 80 years, inclusive, at the time of consent
2. Diagnosis of CSU (presence of urticaria on most days of the week, for a duration of 6 weeks or longer, at any time before Screening) for ≥ 6 months
3. Must be on daily stable doses of H1AH consistent with standard of care for CSU starting at least 3 consecutive days immediately prior to the Screening Visit and willing to remain on stable doses through the Safety Follow-Up Visit
4. Current H1AH treatment up to 4 times the approved dose per local treatment guidelines
5. UAS7 ≥ 16 during the 7 days prior to randomization (Day 1) (data from at least 4 of the 7 days are required to be considered an acceptable profile)
6. If female, must have a negative serum pregnancy test at Screening, be willing to not donate eggs from Screening until 12 weeks after the last dose of study drug, and:
 - a. Is surgically sterile; or
 - b. Has been amenorrhoeic for ≥ 1 year without an alternative medical cause; or

- c. If of childbearing potential³, must agree to use 2 forms of contraception, which includes at least 1 form of highly effective and 1 effective method⁴ of contraception from Screening until 12 weeks after the last dose of study drug. The following methods can achieve a failure rate of less than 1% per year when used consistently and correctly and are considered highly effective birth control methods:
 - Combined (estrogen and progestogen containing) hormonal contraception associated with inhibition of ovulation
 - Progestogen only hormonal contraception associated with inhibition of ovulation
 - Intrauterine device
 - Intrauterine hormone releasing system
 - Bilateral tubal occlusion
 - Vasectomized partner who has received a medical assessment of surgical success
 - Sexual abstinence (complete sexual abstinence defined as refraining from heterosexual intercourse for the entire period of risk associated with study drug), the reliability of which needs to be evaluated in relation to the duration of the clinical study and the preferred and usual lifestyle of the subject

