12.6. Physical Examinations

Physical examinations will include but are not limited to an assessment of general appearance, skin, HEENT (head, eyes, ears, nose, throat), musculoskeletal, thyroid/endocrine, cardiovascular, chest/lung, neurologic, abdomen, and extremities/general body systems.

Symptom directed physical examinations to assess clinically significant changes from Screening or any new signs or symptoms may be conducted at other visits as determined by the Investigator based on subject complaint.

Clinically significant abnormalities from before signing of the ICF will be recorded as medical history, and clinically significant changes after signing the ICF will be recorded as AEs.

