16.9. Safety Analysis

The Safety Analysis Set will be used for the summaries of the safety data. Safety data will be summarized by treatment group and overall.

The safety and tolerability of EP262 will be assessed by comparing the frequency, causality, and severity of AEs as well as treatment discontinuations due to AEs. AEs will be coded using the Medical Dictionary for Regulatory Activities (MedDRA) by System Organ Class and preferred term. AEs that begin after the first administration of study drug, or existing AEs that worsen after the first dose of study drug, are considered treatment emergent. All AE summaries will include TEAEs, and all AEs will be presented in data listings.

Concomitant medications will be coded using the World Health Organization (WHO) Drug Dictionary and summarized descriptively by Anatomic Therapeutic Chemistry (ATC) class using counts and percentages. Medications started prior to the first dose of study drug will be indicated in the data listings. Use of rescue medications will also be summarized.

Changes in vital signs, standard 12-lead ECGs, and laboratory evaluations will be summarized descriptively.

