#### ***3.4.2.1 Adverse Events***

An AE is defined as any untoward medical occurrence in a subject administered a pharmaceutical product and which does not necessarily have a causal relationship with this treatment. An AE can therefore be any unfavorable or unintended sign (including a clinically significant abnormal laboratory finding), symptom, or disease temporally associated with the use of a medicinal (investigational) product.

Medical conditions present at baseline that worsen in severity or frequency after exposure to study drug are considered treatment-emergent AEs (TEAEs). A TEAE is any condition that was not present prior to treatment with the study drug but appeared following treatment, was present at treatment initiation but worsened during treatment, or was present at treatment initiation but resolved and then reappeared while the individual was on treatment (regardless of the intensity of the AE when the treatment was initiated). Planned hospital admissions or surgical procedures for an illness or a disease that existed before administration of study drug, and for which the condition

has not worsened since starting study drug, are not to be considered TEAEs/treatment-emergent serious adverse events (SAEs). Events with emergency room visits that are less than 24 hours will also not be considered SAEs unless they meet one of the criteria listed in Section 12.2.1 of the clinical study protocol.

Clinically significant abnormal laboratory tests, 12-lead ECG assessments, or vital sign results may constitute an AE if they meet one of the criteria listed in Section 12.1.4.1 of the clinical study protocol. However, whenever possible, the underlying diagnosis should be listed in lieu of associated abnormal results. Abnormalities deemed not clinically significant by the Investigator should not be reported as AEs.

AEs are graded for severity (i.e., intensity) using Common Terminology Criteria for Adverse Events (CTCAE), version 5.0 ([HHS 2017](#)). A severity category of mild, moderate, severe, life-threatening, or death, as defined in Appendix B of the clinical study protocol, must be entered on the AE electronic case report form (eCRF).

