#### **4.5.3 Adverse Events**

Treatment-emergent adverse events (TEAEs) are defined as those AEs with onset after the first dose of study drug or existing events that worsened after the first dose during the study. Treatment-emergent AEs will be summarized by treatment group within each study part, pooled treatment groups, and over all subjects combined. Events reported with a partial onset date (e.g., month and year are reported but the day is missing) will be considered to be treatment-emergent if it cannot be confirmed that the event onset was prior to the first dose of study drug based on the available date entries.

Verbatim terms on case report forms will be mapped to preferred terms and system organ classes using MedDRA, version 26.0.

Summaries that are displayed by system organ class and preferred terms will be ordered by descending incidence of system organ class and preferred term within each system organ class. Summaries displayed by preferred term only will be ordered by descending incidence of preferred term. Summaries of the following types will be presented:

- Overall summary of number of unique TEAEs and treatment-emergent serious adverse events (SAEs) and subject incidence of TEAEs meeting various criteria;
- Subject incidence of TEAEs by MedDRA system organ class and preferred term;

- Subject incidence of the most frequently-occurring TEAEs (i.e., TEAEs occurring in  $\geq 10\%$  of the Safety Analysis Set) by MedDRA preferred term;
- Subject incidence of TEAEs by severity grade, MedDRA system organ class, and preferred term;
- Subject incidence of TEAEs by relationship to study drug, MedDRA system organ class, and preferred term;
- Subject incidence of the most frequently-occurring TEAEs related to study drug (i.e., related TEAEs occurring in  $\geq 10\%$  of the Safety Analysis Set) by MedDRA preferred term;
- Subject incidence of severe TEAEs related to study drug by MedDRA system organ class and preferred term; and
- Subject incidence of SAEs by MedDRA system organ class and preferred term.

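### Worsening of CSU itself counts as a TEAE, so the pooled TEAE rows mix efficacy with harm; summaries without CSU terms should be added

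*Protocol*

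**What the plan says.** Protocol 12.1.1 gives the rule: "Medical conditions present at baseline that worsen in severity or frequency after exposure to study drug are considered TEAEs". It also counts a condition that resolves and comes back on treatment, whatever its intensity at the start. SAP 3.4.2.1 repeats both clauses. SAP 4.5.3, which governs the tables, counts AEs with onset after the first dose and "existing events that worsened after the first dose during the study".

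Every subject enters with active disease: Protocol 8.1 requires a UAS7 of at least 16 in the week before randomization. Skin is part of the physical examination, and Protocol 12.6 adds that "clinically significant changes after signing the ICF will be recorded as AEs". Under Protocol 12.1.4 and 12.1.4.1, AEs are collected until the end of study participation and each reoccurrence of a recurrent AE is recorded. Protocol 12.1.3 lets an event be called related even where underlying disease may have produced it.

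Type, frequency and severity of TEAEs are a secondary endpoint compared with placebo (Protocol 6). Protocol 16.9 states the method: "The safety and tolerability of EP262 will be assessed by comparing the frequency, causality, and severity of AEs", together with treatment discontinuations due to AEs. SAP 4.5.3 plans an overview, then tables by system organ class (SOC) and preferred term, by severity and by relationship.

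No visible passage exempts CSU or lack of efficacy, says when CSU counts as worsened, or plans a TEAE summary without CSU terms.

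**The concern.** CSU is the one baseline condition that all subjects share. It fluctuates, and the daily UAS already measures it for the primary endpoint. A CSU flare reported as an AE meets the TEAE definition and enters the pooled rows beside events that have nothing to do with the disease.

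Those pooled rows are what most readers look at first in a tolerability comparison. If EP262 reduces disease activity, fewer subjects on active drug have a CSU event during treatment, and the difference from placebo in the any-TEAE row is pulled towards or past zero. The same applies to overall severity, overall relatedness and discontinuation due to AEs. The planned tables do not allow the any-TEAE row to be split afterwards, because a subject with both a CSU event and another event is counted once. For urticaria, pruritus or angioedema caused by the drug, even the preferred-term rows cannot separate drug effect from disease.

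**Working it through.** **1. The plan's own figure.** Protocol 16.4 and SAP 4.6 give an 8-point difference, SD 13 and 2-sided alpha 10%, with 34 per group in Part 1 and 27 versus 43 for the 25 mg comparison, for 80% power.
- Part 1: Phi(8 / (13 × √(1/34 + 1/34)) − 1.645) = Phi(2.537 − 1.645) = 81.4%.
- Part 2: Phi(8 / (13 × √(1/27 + 1/43)) − 1.645) = Phi(2.506 − 1.645) = 80.5%.
- The noncentral t gives 80.7% and 79.9%.

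The stated 80% reproduces. The documents give no TEAE rate, so every TEAE rate below is an assumption.

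**2. Share of subjects worse than baseline at Week 6.** With normally distributed changes and EP262 8 points better than placebo, q = 1 − Phi(−mean change / 13). The placebo mean change is assumed.

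| Placebo mean change | q placebo | q EP262 | Gap (points) |
|---|---|---|---|
| −4 | 37.9% | 17.8% | 20 |
| −8 | 26.9% | 10.9% | 16 |
| −12 | 17.8% | 6.2% | 12 |

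**3. Effect on the any-TEAE row.** Let b be the non-CSU TEAE rate in an arm and r the fraction of worsened subjects reported as an AE. Under independence, any-TEAE = 1 − (1 − b)(1 − r × q). Take b = 30% on placebo and 40% on EP262, a true excess of +10 points, with a placebo mean change of −8.

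| r | Placebo | EP262 | Difference seen (points) |
|---|---|---|---|
| 25% | 34.7% | 41.6% | +6.9 |
| 50% | 39.4% | 43.3% | +3.9 |
| 100% | 48.8% | 46.6% | −2.3 |

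Over placebo mean changes of −4 to −12 and r of 25% to 100%, the true +10 appears as anything from +7.8 to −5.9.

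**4. Excess that would be fully cancelled.** This is (1 − b) × [1 − (1 − r × q placebo)/(1 − r × q EP262)], with b = 30%. For placebo mean changes of −4, −8 and −12:
- r = 25%: 3.7, 2.9 and 2.1 points.
- r = 50%: 7.7, 5.9 and 4.2 points.
- r = 100%: 17.1, 12.6 and 8.7 points.

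These are smaller than the gaps of 20, 16 and 12 in step 2, because any-TEAE is a union and the rates do not add.

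**5. A stricter threshold.** SAP 3.4.1.1 takes a 10-point reduction as the minimally important difference in UAS7. Applying 10 points to worsening is an assumption. The shares become 14.1%, 8.3% and 4.5% on placebo against 4.5%, 2.3% and 1.1% on EP262. With a placebo mean change of −8, the true +10 then appears as +8.9, +7.8 or +5.5 at r = 25%, 50% and 100%. The excess fully cancelled at r = 100% falls to 7.0, 4.3 and 2.5 points.

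**6. Direction.** One sentence of Protocol 12.1.1 ties worsening to the treatment period, but SAP 4.5.3 counts anything after the first dose and has no off-treatment cut-off. Flares in the 4 weeks after an effective drug is stopped would add events to the EP262 arms, opposite to steps 3 to 5.

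**The case against.** The strongest reply is that the plan already separates most of what matters. SAP 4.5.3 tabulates severity and relationship by SOC and preferred term, and lists SAEs and AEs leading to interruption or discontinuation. Laboratory, ECG, vital-sign and liver criteria are reported on their own. A liver or gastrointestinal signal keeps its own row. This stands: a reader might infer that the definition hides EP262-caused events in general, but the documents support masking only in the pooled rows and in CSU-like terms.

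Second, nothing turns a diary score into an AE. Examination findings become AEs only if clinically significant, and worsening symptoms have a separate route through rescue medication (Protocol 8.5.2), summarised by arm in SAP 4.5.6.4. This also stands. It is tempting to read the shares in step 2 as TEAE rates, or the gaps as the excess that would be cancelled. Both readings go too far: r is unknown and the rates do not add.

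Third, a bias in favour of EP262 cannot be assumed. It needs an effective drug, and follow-up flares could reverse it. If nearly everyone in both arms qualified through ordinary fluctuation, the gap would also shrink.

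Fourth, the comparisons are descriptive, so no test, error rate or sample size changes. At a 30% rate the standard error of a 38-versus-48 difference is √(0.3 × 0.7 × (1/38 + 1/48)), about 10 points, so much of the illustrated distortion lies within sampling noise. That limits the weight of the point but does not make the pooled rows interpretable.

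Last, the reporting convention may sit in site or eCRF training or the Investigator's Brochure. With about 64 sites planned, differing practice is plausible, but the visible documents do not show it.

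**Conclusion.** The concern holds in a limited form. By the wording of both documents CSU worsening is a TEAE, nothing visible exempts it, and the pooled rows compared with placebo therefore mix efficacy with harm to whatever extent sites report it. Those rows cannot be separated from the planned tables. Under the plan's 8-point effect and SD 13, with the assumed rates in step 3, a true 10-point excess is diluted to about 7 points at 25% reporting and changes sign only near full reporting; a stricter threshold dilutes it less. The result rests on an assumed placebo change, assumed TEAE rates, normality, independence and an unknown reporting fraction. It illustrates the mechanism and does not predict the trial's result.

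Two stronger conclusions are not supported: that the TEAE comparison is biased towards EP262 in a known direction, and that non-CSU TEAEs should become the sole basis for judging tolerability. The second would take urticaria and pruritus, and possibly angioedema, out of the main safety contrast, where a urticarial drug reaction would appear. This is an inexpensive improvement in reporting; no planned inference fails without it.

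**What to change.** In SAP 4.5.3:
- Keep all the all-TEAE tables as planned.
- Add supplementary TEAE overview, by-severity and by-relationship summaries that exclude a listed set of preferred terms for CSU and its symptoms.
- Show those CSU terms as their own row, split into on-treatment and follow-up.
- State that the two versions are read together, so that a urticarial drug reaction stays on display.

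Fix the term list before the Part 1 interim. SAP 4.4.6.3 unblinds Part 1 assignments to the study team at that point, and a list drawn up later would be post hoc.

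The cost is a short SAP edit and one extra set of AE tables; no new data are needed.
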